8.3 ADVERSE EVENTS AND SERIOUS ADVERSE EVENTS

8.3.1 DEFINITION OF ADVERSE EVENTS (AE)

Adverse event means any untoward medical occurrence associated with the use of an intervention in humans, whether or not considered intervention-related (21 CFR 312.32 (a)).

8.3.2 DEFINITION OF SERIOUS ADVERSE EVENTS (SAE)

An adverse event (AE) or suspected adverse reaction is considered "serious" if, in the view of either the investigator or sponsor, it results in any of the following outcomes: death, a life-threatening adverse event, inpatient hospitalization or prolongation of existing hospitalization, a persistent or significant incapacity or substantial disruption of the ability to conduct normal life functions, or a congenital anomaly/birth defect. Important medical events that may not result in death, be life-threatening, or require hospitalization may be considered serious when, based upon appropriate medical judgment, they may jeopardize the participant and may require medical or surgical intervention to prevent one of the outcomes listed in this definition. Examples of such medical events include allergic bronchospasm requiring intensive treatment in an emergency room or at home, blood dyscrasias or convulsions that do not result in inpatient hospitalization, or the development of drug dependency or drug abuse.

8.3.3 CLASSIFICATION OF AN ADVERSE EVENT

8.3.3.1 SEVERITY OF EVENT

For adverse events (AEs) not included in the protocol defined grading system, the following guidelines will be used to describe severity.

- **Mild** – Events require minimal or no treatment and do not interfere with the participant’s daily activities.
- **Moderate** – Events result in a low level of inconvenience or concern with the therapeutic measures. Moderate events may cause some interference with functioning.
- **Severe** – Events interrupt a participant’s usual daily activity and may require systemic drug therapy or other treatment. Severe events are usually potentially life-threatening or incapacitating. Of note, the term “severe” does not necessarily equate to “serious”.

8.3.3.2 RELATIONSHIP TO STUDY INTERVENTION

All adverse events (AEs) must have their relationship to study intervention assessed by the clinician who examines and evaluates the participant based on temporal relationship and his/her clinical judgment. The degree of certainty about causality will be graded using the categories below. In a clinical trial, the study product must always be suspect.

- **Definitely Related** – There is clear evidence to suggest a causal relationship, and other possible contributing factors can be ruled out. The clinical event, including an abnormal laboratory test result, occurs in a plausible time relationship to study intervention administration and cannot be explained by concurrent disease or other drugs or chemicals. The response to withdrawal of the study intervention (dechallenge) should be clinically plausible. The event must be pharmacologically or phenomenologically definitive, with use of a satisfactory rechallenge procedure if necessary.
- **Probably Related** – There is evidence to suggest a causal relationship, and the influence of other factors is unlikely. The clinical event, including an abnormal laboratory test result, occurs within a reasonable time after administration of the study intervention, is unlikely to be attributed to concurrent disease or other drugs or chemicals, and follows a clinically reasonable response on withdrawal (dechallenge). Rechallenge information is not required to fulfill this definition.
- **Potentially Related** – There is some evidence to suggest a causal relationship (e.g., the event occurred within a reasonable time after administration of the trial medication). However, other factors may have contributed to the event (e.g., the participant’s clinical condition, other concomitant events). Although an AE may rate only as “possibly related” soon after discovery, it can be flagged as requiring more information and later be upgraded to “probably related” or “definitely related”, as appropriate.
- **Unlikely to be related** – A clinical event, including an abnormal laboratory test result, whose temporal relationship to study intervention administration makes a causal relationship improbable (e.g., the event did not occur within a reasonable time after administration of the study intervention) and in which other drugs or chemicals or underlying disease provides plausible explanations (e.g., the participant’s clinical condition, other concomitant treatments).
- **Not Related** – The AE is completely independent of study intervention administration, and/or evidence exists that the event is definitely related to another etiology. There must be an alternative, definitive etiology documented by the clinician.

8.3.3.3 EXPECTEDNESS

The principal investigator will be responsible for determining whether an adverse event (AE) is expected or unexpected. An AE will be considered unexpected if the nature, severity, or frequency of the event is not consistent with the risk information previously described for the study intervention.

8.3.4 TIME PERIOD AND FREQUENCY FOR EVENT ASSESSMENT AND FOLLOW-UP

The occurrence of an adverse event (AE) or serious adverse event (SAE) may come to the attention of study personnel during study visits and interviews of a study participant presenting for medical care, or upon review by a study monitor.

All AEs including local and systemic reactions not meeting the criteria for SAEs will be captured on the appropriate case report form (CRF). Information to be collected includes event description, time of onset, clinician's assessment of severity, relationship to study product (assessed only by those with the training and authority to make a diagnosis), and time of resolution/stabilization of the event. All AEs occurring while on study must be documented appropriately regardless of relationship. All AEs will be followed to adequate resolution.

Any medical condition that is present at the time that the participant is screened will be considered as baseline and not reported as an AE. However, if the study participant's condition deteriorates at any time during the study, it will be recorded as an AE.

Changes in the severity of an AE will be documented to allow an assessment of the duration of the event at each level of severity to be performed. AEs characterized as intermittent require documentation of onset and duration of each episode.

The principal investigator will record all reportable events with start dates occurring any time after informed consent is obtained until 7 (for non-serious AEs) or 30 days (for SAEs) after the last day of study participation. At each study visit, the investigator will inquire about the occurrence of AE/SAEs since the last visit. Events will be followed for outcome information until resolution or stabilization.

8.3.5 ADVERSE EVENT REPORTING

Adverse events will be reported to the Washington University IRB according to the timeframes set forth by the IRB:

- An event that meets the definition of an unanticipated problem involving risk to participants or others and results in the death of a participant: will be reported within 1 working day.
- An event that meets the definition of an unanticipated problem involving risk to participants or others and does NOT result in the death of a participant: will be reported within 10 working days.
- Adverse events and serious adverse events that do not also meet the definition of an unanticipated problem involving risks to participants or others: will be reported annually during continuing review.
- An unexpected adverse drug event that result in the death of a participant: will be reported within 1 working day.
- An unexpected adverse drug events that does NOT result in the death of a participant: will be reported within 10 working days.

8.3.6 SERIOUS ADVERSE EVENT REPORTING

The study clinician will immediately report to the sponsor any serious adverse event, whether or not considered study intervention related, including those listed in the protocol or investigator brochure and must include an assessment of whether there is a reasonable possibility that the study intervention caused the event. Study endpoints that are serious adverse events (e.g., all-cause mortality) must be reported in accordance with the protocol unless there is evidence suggesting a causal relationship between the study intervention and the event (e.g., death from anaphylaxis). In that case, the investigator must immediately report the event to the sponsor.

All serious adverse events (SAEs) will be followed until satisfactory resolution or until the site investigator deems the event to be chronic or the participant is stable. Other supporting documentation of the event may be requested by the study sponsor and should be provided as soon as possible.

8.3.7 REPORTING EVENTS TO PARTICIPANTS

Individual participants will be notified of any serious, unanticipated adverse events probably related to study interventions.

8.3.8 EVENTS OF SPECIAL INTEREST

Not applicable

8.3.9 REPORTING OF PREGNANCY

Not applicable

8.4 UNANTICIPATED PROBLEMS

8.4.1 DEFINITION OF UNANTICIPATED PROBLEMS (UP)

The Office for Human Research Protections (OHRP) considers unanticipated problems involving risks to participants or others to include, in general, any incident, experience, or outcome that meets all of the following criteria:

- Unexpected in terms of nature, severity, or frequency given (a) the research procedures that are described in the protocol-related documents, such as the Institutional Review Board (IRB)-approved research protocol and informed consent document; and (b) the characteristics of the participant population being studied;
- Related or possibly related to participation in the research (“possibly related” means there is a reasonable possibility that the incident, experience, or outcome may have been caused by the procedures involved in the research); and
- Suggests that the research places participants or others at a greater risk of harm (including physical, psychological, economic, or social harm) than was previously known or recognized.

8.4.2 UNANTICIPATED PROBLEM REPORTING

The investigator will report unanticipated problems (UPs) to the reviewing Institutional Review Board (IRB). The UP report will include the following information:

- Protocol identifying information: protocol title and number, PI’s name, and the IRB project number;
- A detailed description of the event, incident, experience, or outcome;

- An explanation of the basis for determining that the event, incident, experience, or outcome represents an UP;
- A description of any changes to the protocol or other corrective actions that have been taken or are proposed in response to the UP.

To satisfy the requirement for prompt reporting, UPs will be reported using the following timeline:

- UPs involving risk to participants or others and results in the death of a participant will be reported to the IRB within 1 working day.
- UPs involving risk to participants or others and does NOT result in the death of a participant will be reported to the IRB within 10 working days.

8.4.3 REPORTING UNANTICIPATED PROBLEMS TO PARTICIPANTS

Participants will be informed of UPs if/when recommended by the IRB.

9 STATISTICAL CONSIDERATIONS

9.1 STATISTICAL HYPOTHESES

The primary endpoints of this trial will be descriptive outcomes measuring feasibility rather than hypothesis-driven efficacy outcomes. The primary endpoints will include

- Primary Endpoint 1: Fraction of approached patients who enroll in the trial
- Primary Endpoint 2: Fraction of planned study medication infusions that are completed
- Primary Endpoint 3: Fraction of participants with MADRS scores available at all specified time points

The secondary endpoints of this trial will be efficacy outcomes, designed to test the following hypotheses with two-sided superiority comparisons. This feasibility trial is intended to provide estimates of effect sizes, but it will not be powered to test these hypotheses.

- Secondary Endpoint 1: Change in MADRS score between the preoperative assessment and post-infusion day 4
 - Null Hypothesis: The change in MADRS score will be the same in the ketamine group and in the control group.
 - Alternative Hypothesis: The change in MADRS score will be smaller in the ketamine group than in the control group.
- Secondary Endpoint 1: Delta sleep ratio on EEG obtained on the second night following the study medication infusion
 - Null Hypothesis: There will be no difference in delta sleep ratio between the ketamine group and the control group.
 - Alternative Hypothesis: The delta sleep ratio will be greater in the ketamine group compared to the control group.

9.2 SAMPLE SIZE DETERMINATION

The sample size of 32 has been selected to allow the primary descriptive endpoints to be measured with acceptable levels of precision:

- Primary Endpoint 1: Fraction of approached patients who enroll in the trial

- Conservatively assuming that 25% of approached patients will enroll, then $n = 32$ patients will allow this proportion to be measured with a 95% confidence interval width of $\pm 15\%$:

$$95\%CI = \pm 1.96 \sqrt{\frac{p(1-p)}{n}} = \pm 1.96 \sqrt{\frac{(0.25)(0.75)}{32}} = \pm 0.15$$

- Primary Endpoint 2: Fraction of planned study medication infusions that are completed
 - If we assume that 90% of planned infusions are completed, then $n = 32$ patients will allow this proportion to be measured with a 95% confidence interval width of $\pm 10\%$:

$$95\%CI = \pm 1.96 \sqrt{\frac{p(1-p)}{n}} = \pm 1.96 \sqrt{\frac{(0.90)(0.10)}{32}} = \pm 0.10$$

- Primary Endpoint 3: Fraction of participants with MADRS scores available at all specified time points
 - If we assume that 95% of participants will have scores available at all specified time points, then $n = 32$ patients will allow this proportion to be measured with a 95% confidence interval width of $\pm 7\%$:

$$95\%CI = \pm 1.96 \sqrt{\frac{p(1-p)}{n}} = \pm 1.96 \sqrt{\frac{(0.95)(0.05)}{32}} = \pm 0.07$$

This sample size does not provide power to test the secondary endpoints for superiority. However, the observed values will be used to determine effect sizes, as well as standard deviations for the observed values. These quantities will inform the sample size calculation for the full-scale clinical trial. A minimum of 24-30 patients has previously been recommended for estimating effects sizes,^{61,62} so this feasibility trial should be large enough to provide the necessary estimates.

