3 OBJECTIVES AND ENDPOINTS

OBJECTIVES	ENDPOINTS	JUSTIFICATION FOR ENDPOINTS
Primary		
To evaluate the feasibility of recruiting participants to the randomized trial.	Fraction of patients approached who enroll and are randomized.	This endpoint provides an evaluation of how long it would take to

OBJECTIVES	ENDPOINTS	JUSTIFICATION FOR ENDPOINTS
		complete enrollment in a full-scale clinical trial.
To evaluate the feasibility of delivering the study medication.	Fraction of randomized patients who complete the study medication infusion.	This endpoint provides an evaluation of whether infusions were missed for logistical reasons and whether infusions were stopped early due to side effects.
To evaluate the feasibility of collecting participant outcomes.	Fraction of randomized patients with Montgomery-Asberg Depression Rating Scale (MADRS) scores available at all specified time points.	This endpoint provides an evaluation of whether the primary outcome for the full-scale clinical trial can be measured.
Secondary		
To estimate the effect size for the difference in postoperative depressive symptoms between patients receiving ketamine and patients receiving placebo.	Change in MADRS score between the preoperative assessment and post-infusion day 4	The MADRS is a reliable, valid measurement tool for depressive symptoms.
To estimate the effect size for the difference in delta sleep ratio between the intervention and control groups.	Delta sleep ratio on EEG obtained on post-infusion night 1	The delta sleep ratio, defined as the ratio between 1-4 Hz SWA during the first and second non-rapid eye movement epochs during sleep, has previously been associated with ketamine responsiveness.

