5.5 STRATEGIES FOR RECRUITMENT AND RETENTION

Anticipated Patient Population – The target sample size will be 32 patients. Patients will be enrolled at a single site (BJH/Washington University School of Medicine). The expected accrual rate was estimated by examining characteristics (obtained via Epic Slicer Dicer at the population level only) of a retrospective cohort of patients who had non-emergent surgery at BJH between 1/1/2021 and 6/30/2021, had an ICU admission, and had an ICD grouper corresponding to depression documented in the diagnosis list or the past medical history. The query was limited to the cardiac, neurosurgery, and vascular services because many of the patients from other services (e.g., trauma, orthopedic) were suspected to have initially had emergent surgery followed by an ICU admission and then a non-emergent surgery. Exclusion criteria for the retrospective query included age < 18. During that 6-month time period, there were 307 patients who met these criteria (Figure 2). If we conservatively estimate that 20% of these patients enroll in the trial, that results in an accrual of 10 patients per month.

The gender, race and ethnicity, and age distributions are expected to follow the gender, race and ethnicity, and age distributions served by the Barnes-Jewish Hospital. These distributions were observed in the retrospective cohort seen in Figure 2. The anticipated characteristics of the study population are shown in Table 1.

[figure not shown]

Figure 2. Number of potentially eligible patients in a 6-month period.

Table 1. Anticipated Demographic Characteristics of the Study Population

Racial Categories	Ethnic Categories				Total	
	Not Hispanic or Latino		Hispanic or Latino			
	Female	Male	Female	Male		

American Indian/ Alaska Native	1	0	0	0	1
Asian	1	0	0	0	1
Native Hawaiian or Other Pacific Islander	0	0	0	0	0
Black or African American	2	2	0	0	4
White	13	11	1	1	26
More than One Race	0	0	0	0	0
Total	17	13	1	1	32

Recruitment Strategy – Patients will primarily be recruited at the Center for Preoperative Assessment and Planning (CPAP). Potentially eligible patients will be identified by screening the CPAP schedule. Patients identified via screening will be approached by telephone prior to their CPAP appointment or in person at CPAP.

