9.3 POPULATIONS FOR ANALYSES

The population for Primary Endpoint 1 will include all patients who are approached for enrollment in the trial. Primary Endpoints 2 and 3 will be analyzed in an intention-to-treat population that includes all patients who are randomized. The secondary endpoints will also be analyzed in the intention-to-treat population of all patients who are randomized.

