9.4.2 ANALYSIS OF THE PRIMARY EFFICACY ENDPOINT(S)

Primary Endpoint 1:

The fraction of approached patients who enroll in the trial will be described using a proportion. A 95% confidence interval will be used to present uncertainty around this proportion.

The numerator will include all participants who are randomized to receive either ketamine or the placebo.

The denominator will include all patients who are approached by the research team to evaluate eligibility and offer consent. This will include patients approached by telephone in advance of their CPAP appointment, patients approached in person at CPAP, and patients approached in person in the hospital prior to the day of surgery.

Primary Endpoint 2:

The fraction of randomized participants who complete the study medication infusion will be described using a proportion. A 95% confidence interval will be used to present uncertainty around this proportion.

The numerator will include all participants who receive the study medication for at least 7 of the planned 8 hours (if enrolled under protocol version 1) or for at least 2 of the planned 3 hours (if enrolled under protocol version 2). If the study medication is temporarily halted but later restarted, the participant will still be included in the numerator if the total time with an active infusion is above the threshold defined above.

The denominator will include all participants who are randomized to receive either ketamine or the placebo.

Primary Endpoint 3:

The fraction of participants with MADRS scores available at all the specified time points will be described using a proportion. A 95% confidence interval will be used to present uncertainty around this proportion.

The numerator will include all participants with MADRS scores documented at all of the following time points: preoperative baseline, post-infusion days 1, 2, 4, 7, and 14.

The denominator will include all participants who are randomized to receive either ketamine or the placebo.

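### Section 9.2 computes the precision of Primary Endpoint 1 with the 32 patients to be randomised instead of the number approached; at the assumed 25% the half-width is about ±7.5%, not ±15%

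*Combined protocol and SAP*

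**What the plan says.** Section 9.2 says that 32 was chosen so that the three descriptive primary endpoints are estimated with acceptable precision, and it gives one calculation for each. The first assumes that "25% of approached patients will enroll, then $n = 32$ patients will allow this proportion to be measured" with a 95% half-width of ±15%, from 1.96 × √(0.25 × 0.75/32).

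The endpoint itself is defined elsewhere in the same document:

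- Section 9.3: "The population for Primary Endpoint 1 will include all patients who are approached for enrollment in the trial".
- Section 9.4.2, numerator: "The numerator will include all participants who are randomized to receive either ketamine or the placebo".
- Section 9.4.2, denominator: "The denominator will include all patients who are approached by the research team to evaluate eligibility and offer consent".

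Section 5.5 shows what the 32 is: "The target sample size will be 32 patients". Section 9.2 uses the same 32 for Primary Endpoints 2 and 3, and Sections 9.3 and 9.4.2 give both of those a denominator of randomised participants.

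**The concern.** In a binomial precision formula, n is the denominator of the proportion. For Primary Endpoint 1 that is the number approached. Section 9.2 enters the planned number randomised, which is the endpoint's expected numerator.

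The figure matters because it is one of the three on which the sample size is justified. Section 3 also ties the endpoint to planning the next trial: "This endpoint provides an evaluation of how long it would take to" complete enrolment at full scale. A reader of Section 9.2 would expect an interval of about 10% to 40% around an enrolment fraction of 25%, which is weak information for that purpose. The planned 32 randomised patients imply a considerably tighter interval.

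**Working it through.** **Inputs**

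- Assumed proportion p = 0.25 (Section 9.2: "Conservatively assuming that 25% of approached patients will enroll").
- n in the plan's formula = 32 (Section 9.2), the target sample size (Section 5.5).
- Two-sided 95% confidence, z = 1.96 (Section 9.2; Section 9.4.2 also specifies a 95% interval).
- Endpoint = randomised / approached (Section 9.4.2).

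**Step 1. Reproduce the stated figure.**
Half-width = z × √(p(1 − p)/n) = 1.96 × √(0.25 × 0.75/32) = 0.1500. This matches ±15% and gives an interval of 10.0% to 40.0%. The arithmetic is sound for n = 32.

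**Step 2. Can 32 be the number approached?**
If 32 were approached, 0.25 × 32 = 8 would be randomised. That contradicts the target of 32 and leaves 8, not 32, for the Endpoint 2 and 3 calculations in the same section. The three calculations cannot all hold with n = 32.

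**Step 3. Use the plan's own denominator.**
Number approached = 32/0.25 = 128.
Half-width = 1.96 × √(0.25 × 0.75/128) = 0.0750, or ±7.5%, giving 17.5% to 32.5%.
The ratio to the stated figure is √(32/128) = 0.5.

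**Step 4. Does the interval method matter?**
For 32 randomised out of 128 approached:

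| Method | 95% interval |
|---|---|
| Wald (the plan's formula) | 17.5% to 32.5% |
| Wilson | 18.3% to 33.2% |
| Clopper-Pearson | 17.8% to 33.4% |

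If recruitment is treated as inverse sampling (approach patients until 32 are randomised), the approximate half-width is 1.96 × p × √((1 − p)/32) = 1.96 × 0.25 × √(0.75/32) = 0.0750, the same value.

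**Step 5. Express it as approaches per randomised patient (1/p).**

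- As stated: 1/0.400 = 2.5 to 1/0.100 = 10.0, a 4.0-fold range.
- Corrected: 1/0.325 = 3.1 to 1/0.175 = 5.7, a 1.9-fold range.

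**Step 6. Sensitivity to the assumed fraction, with 32 randomised.**
The 20% and 30% below are assumptions made for this check.

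| Fraction randomised | Approached | Half-width |
|---|---|---|
| 20% | 160 | ±6.2% |
| 25% (the plan) | 128 | ±7.5% |
| 30% | about 107 | ±8.7% |

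Section 5.5 does mention 20%, but as a share of a retrospective cohort of 307 potentially eligible patients. It is not a fraction of patients approached, so it does not replace the 25%.

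**The case against.** The strongest case against acting is that nothing downstream depends on this number. The primary endpoints are descriptive, and the documents set no progression threshold for Endpoint 1. Section 9.4.2 bases the final interval on the patients actually approached, so the reported result would be correct even if Section 9.2 were left alone. The full-scale trial would be planned from the observed interval, not from this one, and its duration also depends on how many patients can be approached per month, which a proportion does not measure. All of this stands. It limits the consequence but does not make ±15% a correct statement of planned precision.

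A second objection concerns the replacement figure. Section 9.2 says enrol, Section 9.4.2 counts randomised participants, and Section 5.4 recognises patients who consent but are never randomised. If the 25% meant consent, more than 128 approaches would be needed. Assuming that 10% to 30% of consenting patients are not randomised (the documents give no figure):

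- 10%: 32/(0.25 × 0.90) = about 142 approached, p = 0.225, half-width ±6.9%.
- 30%: 32/(0.25 × 0.70) = about 183 approached, p = 0.175, half-width ±5.5%.

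Section 7.2 also lets patients who are randomised but untreated be replaced, which could take the number randomised slightly above 32 and tighten the interval further. So ±7.5% is conditional on how the 25% is read. Both alternatives move further from ±15%, and no reading consistent with 32 randomised recovers it.

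**Conclusion.** The concern holds. The fault lies in the input, not in the calculation: Section 9.2 uses the endpoint's planned numerator as its binomial denominator, in conflict with Sections 9.3 and 9.4.2. At the plan's own 25%, the stated half-width is twice what the design implies (±15.0% against ±7.5%).

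The ±7.5% assumes that the 25% means randomised over approached, as the Section 9.4.2 numerator implies, and that 32 patients are randomised in the end. The error is in the safe direction and gives no reason to change the sample size. It should be corrected because the figure is a stated precision for a primary endpoint and part of the sample-size justification. The use of n = 32 is right for Endpoints 2 and 3.

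**What to change.** In Section 9.2, for Primary Endpoint 1 only, replace n = 32 with the expected number approached, 32/0.25 = 128, and replace ±15% with about ±7.5%. Say in the same line that the 25% is the fraction of approached patients who are randomised, so that the 128 can be traced. If a range for other enrolment fractions is added, label those fractions as assumptions.

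Sections 9.3 and 9.4.2 need no change. The cost is one corrected line, with no effect on the design, the patients, the data collected or the analysis.

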9.4 STATISTICAL ANALYSES

9.4.1 GENERAL APPROACH

For descriptive statistics, categorical data will be presented using frequency counts and percentages, normally distributed continuous data will be presented using means and standard deviations, and non-normally distributed continuous data will be presented using medians and interquartile ranges.

Normality will be assessed using visual analysis of histograms and using the Kolmogorov-Smirnov test. All inferential tests will be two-tailed, and p-values < 0.05 will be considered statistically significant.

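### Section 9.2 states ±7% for Primary Endpoint 3 where its own formula gives ±7.6%; that formula passes 100% for Endpoints 2 and 3, and Section 9.4.2 names no interval method

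*Combined protocol and SAP*

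**What the plan says.** Section 9.2 rests the sample size on precision alone: "The sample size of 32 has been selected to allow the primary descriptive endpoints to be measured with acceptable levels of precision". It applies one formula to all three primary endpoints, 1.96 × √(p(1 − p)/n) with n = 32, and reports the result as a symmetric ± figure.

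- Endpoint 1 (enrolment among those approached), p = 0.25: ±15%.
- Endpoint 2 (infusions completed): "If we assume that 90% of planned infusions are completed, then $n = 32$ patients will allow this proportion to be measured" to within ±10%.
- Endpoint 3 (MADRS available at every time point): "If we assume that 95% of participants will have scores available at all specified time points, then $n = 32$ patients will allow" a precision of ±7%.

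For the analysis, Section 9.4.2 repeats one sentence under each primary endpoint: "A 95% confidence interval will be used to present uncertainty around this proportion". It does not say how the interval is computed. Section 9.4.1 says that "categorical data will be presented using frequency counts and percentages" and gives no interval method either. The formula in Section 9.2 is the only one for a proportion anywhere in the document.

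**The concern.** Three things stand out. The ±7% does not follow from the expression printed beside it. The formula relies on a normal approximation that is poor for proportions of 0.90 to 0.95 with 32 patients, where a symmetric interval runs past 100%. And the analysis section leaves the method open, so the planning formula is the natural one to carry forward.

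Section 9.1 describes the primary endpoints as descriptive measures of feasibility, so each proportion and its interval are the whole primary result. For feasibility the lower limit is the informative one: how low could completion of infusions or of MADRS assessment plausibly be? A symmetric ± understates that side. At 32 out of 32, a plausible result, the Wald interval has zero width and would report no uncertainty at all.

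**Working it through.** **Inputs.** From Section 9.2: n = 32, z = 1.96, and assumed proportions of 0.25, 0.90 and 0.95. Sections 9.3 and 9.4.2 take all randomized patients as the denominator for Endpoints 2 and 3.

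**Step 1: reproduce the stated half-widths with 1.96 × √(p(1 − p)/n).**

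| Endpoint | Calculation | Result | Stated |
|---|---|---|---|
| 1 | 1.96 × √(0.25 × 0.75 / 32) | 0.1500 | ±0.15, agrees |
| 2 | 1.96 × √(0.90 × 0.10 / 32) | 0.1039 | ±0.10, agrees after rounding |
| 3 | 1.96 × √(0.95 × 0.05 / 32) | 0.0755 | ±0.07, does not agree |

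For Endpoint 3, other conventions do not give 0.07 either: z = 2 gives 0.0771, t with 31 degrees of freedom 0.0786, n − 1 in the denominator 0.0767, and a 90% level 0.0634. Truncating 0.0755 would give 0.07. A true ±0.07 needs n = 1.96² × 0.0475 / 0.07² = 37.2, that is 38 patients.

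**Step 2: limits implied by the formula.**

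- Endpoint 2: 0.90 ± 0.1039, or 79.6% to 100.4%.
- Endpoint 3: 0.95 ± 0.0755, or 87.4% to 102.6%.

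With n = 32 the upper limit exceeds 1 for any proportion between 32/(32 + 1.96²) = 0.893 and 1.

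**Step 3: Wilson intervals at the same assumptions.** The centre is (p + z²/2n)/(1 + z²/n) and the half-width is z√(p(1 − p)/n + z²/4n²)/(1 + z²/n). With z² = 3.8416: z²/n = 0.12005, z²/2n = 0.060025 and z²/4n² = 0.000938.

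- p = 0.90: centre 0.960025/1.12005 = 0.8571; half-width 1.96 × √(0.0028125 + 0.000938)/1.12005 = 0.1072. Limits 75.0% to 96.4%, which is 15.0 points below and 6.4 above.
- p = 0.95: centre 1.010025/1.12005 = 0.9018; half-width 1.96 × √(0.0014844 + 0.000938)/1.12005 = 0.0861. Limits 81.6% to 98.8%, which is 13.4 points below and 3.8 above.

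Total width changes little: 21.4 against 20.8 points for Endpoint 2, and 17.2 against 15.1 for Endpoint 3. Clopper-Pearson limits are similar: 74.2% to 97.7% and 81.0% to 99.6%.

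**Step 4: coverage if the Section 9.2 formula were also used at analysis.** Binomial probabilities are summed over the outcomes 0 to 32 whose interval contains the true proportion.

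| True proportion | Wald coverage | Lower limit too high | Upper limit too low | Wilson coverage |
|---|---|---|---|---|
| 0.90 | 84.0% | 15.6% | 0.3% | 96.4% |
| 0.95 | 80.2% | 19.4% | 0.5% | 98.0% |

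At 0.95 the 19.4% is the single outcome 32/32 (0.95³² = 0.194), where the Wald interval is 100% to 100%; Wilson gives 89.3% to 100% and Clopper-Pearson 89.1% to 100%. At 0.90 both 32/32 (0.034) and 31/32 (0.122; Wald lower limit 90.85%) miss. Treating 32/32 separately therefore raises coverage there only to 87.5%.

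Coverage moves with the true proportion. In steps of 0.0001 from 0.90 to 0.95, Wald runs from 79.8% to 94.7% (mean 87.9%) and never reaches 95%; Wilson runs from 93.5% to 98.0% (mean 96.4%).

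**The case against.** The case for leaving this alone is mainly about weight.

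- The arithmetic slip is about 0.55 percentage points and probably a truncation. Section 9.2 sets no maximum width, so nothing in the plan fails at ±8%. This stands: the slip alone is a small correction.
- The overshoot for Endpoint 2 appears only with the unrounded half-width; with the stated ±10% the upper limit is exactly 100%. This also stands. For Endpoint 3 the limit exceeds 100% under either figure (102% even with ±7%).
- A normal-approximation half-width is a common planning device and does not commit the analysis to it. That is correct, and the coverage figures apply only if the formula is carried forward. But the plan offers no other formula, and an open choice would be made after the data are seen.
- No feasibility threshold is stated, and readers given the counts can compute any interval they like. No decision can be shown to change. The interval is nonetheless the reported primary result and should be sound as reported.
- The Wilson figures are idealised: 0.90 × 32 = 28.8 and 0.95 × 32 = 30.4 are not possible counts. They are planning values, to be labelled as such. Attainable Wilson intervals nearby are 75.8% to 96.8% (29/32), 79.9% to 98.3% (30/32) and 84.3% to 99.4% (31/32). Section 7.2 also allows replacement of patients randomized but not treated, so the denominator may slightly exceed 32; that does not repair the formula.
- Endpoint 1 has a larger discrepancy: its ±15% uses 32, although its denominator is patients approached, about 32/0.25 = 128 at the plan's own rate, giving about ±7.5%. This is a separate matter that neither weakens nor is settled by the present point.

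**Conclusion.** The point holds. The stated ±7% is wrong by the plan's own formula, which gives ±7.6%. The more important part is the unnamed interval method combined with a planning formula that performs poorly here. At the plan's assumptions the uncertainty below the estimate is about 15 points for Endpoint 2 and 13 for Endpoint 3, against the stated 10 and 7. Using the formula at analysis would give coverage of 84.0% and 80.2% in place of 95%, with nearly all misses being lower limits that are too high, so feasibility would look more certain than the data support.

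These figures assume 32 randomized patients and the plan's proportions of 0.90 and 0.95; the coverage figures further assume that Wald intervals are reported. Total width barely changes, so the choice of 32 is not undermined, and no claim is made about a go/no-go decision. The change should be made because it is nearly free and concerns the primary results.

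**What to change.** In Section 9.2, correct the Endpoint 3 formula result to 0.0755 (±8% rounded) if that calculation is kept. Give the expected precision of Endpoints 2 and 3 as asymmetric Wilson 95% intervals, labelled as planning values at the assumed proportions: about 75% to 96% for Endpoint 2 at 90%, and about 82% to 99% for Endpoint 3 at 95%.

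In Section 9.4.2, add one sentence naming the method for the primary proportions, either Wilson or Clopper-Pearson. Both stay within 0 to 100% and give a usable interval at 32/32. If Clopper-Pearson is chosen, the Section 9.2 figures should be computed the same way (about 74% to 98% and 81% to 100%).

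The cost is one sentence and a few restated figures. The stated precision becomes asymmetric and slightly less favourable. Sample size and trial conduct do not change.
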